4.1.2 Visit Windows

The recommended and allowed intervals between study visits are presented in the protocol Section 7, Study Procedures ([Appendix A](#)). No recalculation of time windows or formal visit windowing will be conducted. By-visit tabular summaries will assume that observations are from the scheduled visit recorded in the eCRF irrespective of the date specified.

4.2 Definition of Populations

4.2.1 All Screened Population

The All Screened Population is defined as all patients who have completed a Screening Visit. The summary of disposition and the listing of inclusion/exclusion criteria not met will be based on the All Screened Population.

4.2.2 All Enrolled Population

The All Enrolled Population is defined as all subjects who receive at least 1 dose of study drug. Analyses and summaries of demographic and Baseline characteristics, safety assessments, and subject reported outcomes will be based on the All Enrolled Population.

4.3 Data Handling Conventions

4.3.1 General Conventions

Data will be analyzed using SAS (Version 9.4 or later). Descriptive analyses will be performed on demographic and baseline characteristics, safety assessments, platelet counts, and subject reported outcomes.

Descriptive statistics will be tabulated as follows:

- Categorical data will be summarized in contingency tables presenting frequencies and percentages, and
- Continuous data will be summarized using number of non-missing values (n), mean, standard deviation, median, minimum, and maximum values.

4.3.2 Definition of Study Day

The first day of study treatment with avatrombopag will be during the Baseline Visit/Visit 2 and will be referenced as Study Day 1. There is no Study Day 0. The day before the first day of study treatment will be Study Day -1. If an event occurs on or after the first day of study treatment, Study Day will be calculated as (Date of Event - Date of first study treatment + 1). If the event occurs prior to the first day of study treatment, Study Day will be calculated as (Date of Event - Date of first study treatment).

Confidential

4.3.3 Definition of Baseline

Baseline is defined as the last non-missing assessment done on or before the start of study treatment on Study Day 1. Assessments done on the date of study treatment administration are assumed to take place before the administration, unless specified otherwise.

4.3.4 Handling Missing Data

All available data will be included in data listings and tabulations.

No imputation of missing data is planned for study endpoints.

4.3.5 Partial Dates

For the purpose of inclusion of appropriate data records in the analysis, some partially missing dates will have date imputation performed. However, these imputations will be limited to table summaries; listings will retain the date as entered in the database. The following imputations will be performed:

Medications:

- If a start date is missing the day
 - Set to the 1st of the month
- If a start date is missing the day and month
 - Set to January 1st if study treatment began the year prior to the year of medication start
 - Set to January 1st if the medication is known to start in a year prior to study treatment
 - If the medication and the study treatment start the same year, the medication start date will be set to the study treatment start date.
- No medication end dates will be imputed
- No completely missing dates will be imputed. If, after imputation, it cannot be determined whether a medication was taken prior or concomitantly, it will be considered a concomitant medication.

Adverse Events:

- If a start date is missing the day
 - Set to the 1st of the month, or the same day as treatment start if it is the same month and year as treatment start
- If a start date is missing the day and month
 - Set to treatment start date if it is the same year as treatment start; otherwise set to January 1st if it is the year after treatment start.
- No adverse event end dates will be imputed
- No completely missing start dates will be imputed. If, after imputation, it cannot be determined if an adverse event is treatment-emergent, it will be considered treatment-emergent for analysis purposes.

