5 SELECTION AND EARLY TERMINATION OF SUBJECTS

5.1 Inclusion Criteria

Subjects who meet all of the following criteria will be eligible to participate:

- 1. Subject is willing and able to provide written informed consent.
- 2. Male or female aged ≥ 18 years of age at the Screening Visit/Visit 1.
- 3. Subject has been undergoing treatment for primary ITP with eltrombopag or romiplostim for at least 90 days prior to the Screening Visit/Visit 1.
- 4. Subject has had a previous response (at any time) to either eltrombopag or romiplostim, defined as at least 2 platelet counts $\geq 50 \times 10^9 / L$.
- 5. Subject is willing and able to comply with all aspects of the protocol, including completing the self-administered TSQM.

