6.4 Administration of Prior TPO-RA

Descriptive statistics of variables related to the administration of prior TPO-RA will be displayed for all enrolled subjects. The table will be divided in 2 sections (one for romiplostim and one for eltrombopag) and include a summary of:

- Duration of prior treatment with romiplostim and eltrombopag (weeks) as a continuous variable
- Most recent dose level of eltrombopag and romiplostim (mg or mcg/kg) as a categorical variable

- Subject-reported responses to the 3 brief questions in the romiplostim and eltrombopag eCRF pages

An additional table will be created comparing the most recent dose level of prior TPO-RA (romiplostim and eltrombopag) recorded at the Baseline Visit to the stable dose of avatrombopag at the end of study. The stable dose of avatrombopag at the end of the study will be defined as the final avatrombopag dose recorded in the eCRF at the End of Study Visit on Day 90. The prior TPO-RA dose will be categorized into 3 dose groups (low, medium, and high), and the table will summarize the stable dose of avatrombopag by prior TPO-RA within each group.

Listings (one for romiplostim and one for eltrombopag) will present each individual subject's duration of prior treatment, most recent dose level (units), date of last dose, and answers to the 3 questions in the romiplostim and eltrombopag eCRF pages.

7. Prior and Concomitant Treatment

Prior and Concomitant medications will be classified according to the World Health Organization (WHO) Drug Dictionary Global (Enhanced w/WHO Herbal Dictionary). The coding version may be updated prior to database lock if a newer version is available. Medications will be coded per the Anatomical Therapeutic Classification (ATC). All medications will be documented from the time of informed consent up to the End of Study/Early Termination Visit.

Prior medications are those which start and stop before the first day of study treatment. Concomitant medications are those which are being taken on or after the first day of study treatment.

Tabular summaries will display the number and percentage of subjects with at least one medication in ATC Level 2 and preferred name categories by prior TPO-RA (romiplostim and eltrombopag) and overall groups. Subjects who have taken a medication more than once will only be summarized once per ATC Level 2 or preferred name.

The tabular summaries to be provided are as follows:

- Prior Medications
- Concomitant Medications

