9.2 Adverse Events

Adverse events (AEs) will be coded using MedDRA version 26.1 or later. The coding may be updated according to newly released versions of the dictionary.

Severity of AEs is categorized according to the following categories as entered in the eCRF: Mild, Moderate, Severe.

For investigator determined relationship to study drug, AEs are classified as "Related" or "Not Related".

AEs leading to discontinuation of avatrombopag are AEs where action taken is designated as "Drug Withdrawn" in the eCRF.

Two categories for Adverse Events of Special Interest (AESI) will be summarized and are defined based on terms in Standardized MedDRA Queries (SMQs) from MedDRA v26.1 or later:

1. Thromboembolic events - Any thrombotic or embolic event, whether arterial or venous – SMQ = Embolic and thrombotic events
2. Bleeding Events - Any clinically significant blood loss [e.g., bleeding events with CTCAE grade 3+ (based on AE severity [AESEV]>=3] – SMQ = Haemorrhage terms (excl laboratory terms)

[figure not shown]
TEAEs are defined as AEs occurring on or after the first dose of study treatment. TEAE will be tabulated by System Organ Class (SOC) and Preferred Term (PT) by prior TPO-RA (romiplostim and eltrombopag) and overall. TEAESI will be tabulated by AESI category and PT. Subjects with more than one TEAE in a SOC or PT will only be counted once per SOC or PT.

An overview summary table will include the number and percentage of all enrolled subjects with at least one:

- TEAE
- Serious TEAE
- TEAE of special interest (thromboembolic events and bleeding events)
- TEAE related to avatrombopag
- Severe TEAEs
- TEAE leading to study drug discontinuation

Summary tables of TEAEs will be provided for:

- TEAE (by SOC and PT)
- Serious TEAE (by SOC and PT)
- TEAE of special interest (by AESI category and PT)
- TEAE related to avatrombopag (by SOC and PT)

- Severe TEAEs (by SOC and PT)
- TEAE leading to study drug discontinuation (by SOC and PT)

Summary tables will also include number of events for each AE by SOC and by PT.

Listings of all adverse events reported after the consent form is signed (both TEAE and non-TEAE) will be provided and will include information such as the patient identifier, SOC, PT, reported term, date of onset/stop, duration of the event, TEAE, seriousness, severity, action taken, outcome, causality and relationship. A flag will be included in the listings to designate whether an adverse event is treatment-emergent.

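### SAP 4.3.5 imputes partial start dates without using a recorded stop date, so an adverse event that resolved before first dose can be counted as treatment-emergent

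*SAP*

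**What the plan says.** **AEs.** SAP 4.3.5 treats a start date with the day missing as follows: "Set to the 1st of the month, or the same day as treatment start if it is the same month and year as treatment start". Where day and month are both missing, the start becomes Day 1 when the year matches the year of first dose. AE end dates are not imputed. SAP 9.2 adds: "TEAEs are defined as AEs occurring on or after the first dose of study treatment". If treatment-emergent status still cannot be determined after imputation, the event is taken as treatment-emergent.

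**Medications.** With the day missing: "Set to the 1st of the month". With day and month missing, in the year of first dose: "the medication start date will be set to the study treatment start date". Medication end dates are not imputed, and a record that cannot be placed goes to concomitant. SAP 7 says: "Prior medications are those which start and stop before the first day of study treatment". Its next sentence makes concomitant those drugs that were being taken on or after Day 1.

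**Scope.** The imputed dates serve the tables only; listings keep the dates as entered. None of these rules refers to a recorded stop date.

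**The concern.** A start date is imputed so that a record can be placed before or after first dose. When a recorded stop date already shows that the event or drug ended before first dose, its placement is known, and the start date has nothing left to decide. The SAP imputes Day 1 anyway. The analysis data can then hold a start date later than the stop date, and the class follows the imputed start.

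This matters most for AEs. Their occurrence is the primary endpoint (SAP 3.2.1), and every AE summary table in SAP 9.2 is built on treatment-emergent events. There is no control arm, so the boundary at first dose is what separates events on the earlier thrombopoietin receptor agonist (TPO-RA) from events on avatrombopag. An event that ended while the subject had not yet taken avatrombopag should not be counted on it. For medications, the tables in SAP 7 are meant to separate finished treatment from co-treatment, and the rule leaves some finished treatments without a class.

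**Working it through.** The plan states no figure on this point, so there is none to reproduce. The check applies the stated rules to example records and then bounds their reach.

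**Inputs**
- Imputation rules and defaults: SAP 4.3.5.
- Definitions: SAP 7 (prior, concomitant) and SAP 9.2 (treatment-emergent AE, TEAE).
- AEs are collected from consent: Protocol 9.1.
- Screening precedes Baseline by at most 28 days, or the visits are combined: Protocol 7.2.
- Planned size: at least 100 subjects, 50 (±10) per prior TPO-RA: Protocol 4.1.

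**Step 1. Apply the rules.** Take Day 1 = 20 June 2022. Every stop date is known and falls before Day 1.

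| | Record | Start as entered | Stop | Imputed start | Start after stop? | Class under the SAP |
|---|---|---|---|---|---|---|
| a | Medication | 2022 | 10 Mar | 20 Jun | yes | neither prior nor concomitant |
| b | Medication | Jun 2022 | 10 Jun | 1 Jun | no | prior (right) |
| c | Medication | Feb 2022 | 10 Mar | 1 Feb | no | prior (right) |
| d | AE | Jun 2022 | 10 Jun | 20 Jun | yes | TEAE (wrong) |
| e | AE | 2022 | 10 Jun | 20 Jun | yes | TEAE (wrong) |
| f | AE | May 2022 | 1 Jun | 1 May | no | not TEAE (right) |

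In d and e the imputed start is 20 − 10 = 10 days after the event ended. The default for undetermined AEs does not come into play, because imputation has already given an answer.

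In a, the Day 1 start fails the prior definition, which needs both start and stop before Day 1. The 10 March stop fails the concomitant definition, because the drug was not being taken on Day 1 or later. The record reaches the concomitant table only through the default, or if a program treats everything that is not prior as concomitant.

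**Step 2. How often a pre-dose AE would meet the Day 1 branch.** Assume Day 1 is spread evenly over a 365-day year. A date j days before Day 1 lies in an earlier month when Day 1 falls on one of the first j days of a month, which is 12j days of 365. Averaging over j = 1 to L, for L up to 28:

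- Same month: 1 − 6(L + 1)/365
- Same year: 1 − (L + 1)/730

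| Screening interval L | Same month as Day 1 | Same year as Day 1 |
|---|---|---|
| 7 days | 1 − 48/365 = 87% | 1 − 8/730 = 99% |
| 14 days | 1 − 90/365 = 75% | 1 − 15/730 = 98% |
| 28 days | 1 − 174/365 = 52% | 1 − 29/730 = 96% |

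So if a pre-dose AE has a missing start day, the Day 1 branch is more likely than not to apply. These are shares of possible onset days, not misclassification rates. The AE must also have a partial start date and a recorded stop before first dose, and the documents give no count of either.

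**Step 3. Size of one error.** One subject is 1/100 = 1 point overall and 1/50 = 2 points in a group of 50 (1/60 = 1.7 to 1/40 = 2.5 points over the planned range). These are upper limits for a row of subject percentages. Subjects count once per system organ class or preferred term, so someone already counted in that row does not move it. The event counts, which SAP 9.2 also asks for, rise by one each time.

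**Step 4. Let the stop date decide first.** Record a becomes prior, and d and e become not treatment-emergent. Records b, c and f do not change.

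**The case against.** **The rule is conservative.** It can only add TEAEs, in line with the SAP's preference for counting unclear events as treatment-emergent, and the safety analysis is descriptive with no test attached. The direction is right. But conservatism is a reason to count events whose timing is unknown, and here the stop date settles the timing.

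**It will be rare.** This stands in large part. An affected AE must begin after consent, because conditions already present at Screening count only if they change (Protocol 9.1). It must begin within 28 days of Day 1, a window near zero when visits are combined, and it must have an incomplete start date that survives data queries (Protocol 11.1.5). For serious events this is less likely still, since a detailed report is due within 24 hours.

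**The listings show the truth.** They keep the dates as entered, so a reader could spot such a record. They also carry a treatment-emergent flag and a prior/concomitant designation. The SAP does not say whether these follow the imputed date; if they do, a listing would show an event that ended before first dose flagged as emergent.

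**The word occurring in SAP 9.2 might exclude an event that has already ended.** A careful programmer could read it so. The definition has no stop-date test, however, and the start is the only AE date that SAP 4.3.5 supplies.

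**Stronger readings that the documents do not support.** A reader might infer that treatments ended before the switch are generally moved to Day 1 and counted as concomitant. Medications missing only the day go to the first of the month and classify correctly, and SAP 7 read literally does not make an ended drug concomitant. A reader might also infer that a Day 1 start for the earlier TPO-RA contradicts inclusion criterion 3 ("Subject has been undergoing treatment for primary ITP with eltrombopag or romiplostim for at least 90 days prior to the Screening Visit/Visit 1"). Sites confirm eligibility at Screening and Baseline, and imputed dates are confined to tables. The qualifying drug's duration, dose and last-dose date are also recorded separately (Protocol 7.2 and 7.3; SAP 6.4).

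**Conclusion.** The gap is real, and it lies mainly on the AE side. As written, SAP 4.3.5 with SAP 9.2 counts an AE as treatment-emergent when its start day is missing in the month of first dose, or only its year is known in the year of first dose, even if its recorded stop date precedes first dose. This is a wrong result from a stated rule, not a missing detail, and it enters the primary-endpoint tables. It can only over-count.

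The medication side is narrower: only year-only starts in the treatment year are affected, and the outcome is a record without a class that becomes concomitant by default.

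The number of affected records cannot be computed from the documents. Given the short pre-dose window and the combination of conditions required, it is probably small; that is a judgement, not a calculation. The effect per subject, at most 1 point overall and about 2 points in a group of 50, assumes the planned enrolment. Nothing here suggests that the study's safety conclusion would change. The case for acting is that the correction is almost free.

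**What to change.** Add to SAP 4.3.5, for AEs and medications alike:

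1. If a full or partial stop date shows that the record ended before first dose, the AE is not treatment-emergent and the medication is prior. This overrides both the Day 1 imputation and the default. For a partial stop date, every date compatible with it must be before Day 1.
2. No imputed start date may be later than the recorded stop date; take the earlier of the two.
3. Keep the conservative default (treatment-emergent, concomitant) when the stop date is missing, the record is ongoing, the stop is on or after Day 1, or the stop is partial and not clearly before Day 1. With Day 1 on 20 June 2022, a stop of May 2022 falls under item 1 and a stop of June 2022 falls here.

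In SAP 7, define a prior medication by its stop date alone: stopped before Day 1. The two classes then leave no gap.

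The cost is a few sentences and one programming condition per domain. Records whose timing is truly unknown are still handled conservatively, so nothing is lost on the safety side.

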4.4 Treatment Groups

All subjects enrolled in the study will receive open-label avatrombopag. Data displays will have three columns for All Enrolled Population, presented by prior

TPO-RA (romiplostim and eltrombopag) and overall, unless otherwise specified in the mock TLFs.

4.5 Data Listings

Data listings will generally include Subject ID, Age, Sex, Race, and as applicable, prior TPO-RA by default.

5. Study Patients

5.1 Disposition of Patients

A summary table by prior TPO-RA (romiplostim and eltrombopag) and overall group will include the total number of subjects screened and the numbers and percentages of screened subjects who enrolled in the study, subjects who failed screening, and the reason for screen failure. In addition, if any subjects are excluded after screening it will be reported as "Post screening exclusion" defined as subjects who screened but not enrolled to study and take medication yet.

The summary table will also contain the numbers and percentages of patients who completed the study, discontinued the study early, and the primary reason for early discontinuation.

A disposition listing will include the verbatim "Other" specified text from the eCRF if the reason for screen failure or the reason for early discontinuation from the study is entered as "Other." If the reason for discontinuation is adverse event, then the listing will display the associated adverse event (AE) preferred term.

5.2 Inclusion and Exclusion Criteria Details

Details of inclusion/exclusion criteria for subjects in the All Screened Population will be provided in a listing. This listing will indicate the protocol version, informed consent date, whether the subject rescreened, and if the subject enrolled. Details of inclusion and exclusion criteria not satisfied for subjects who did not enroll will be provided. The listing will also indicate if the subject's Screening and Baseline visits were combined.

6. Demographic and other Baseline Characteristics

Demographics and Baseline Characteristics will be summarized for subjects by prior TPO-RA (romiplostim and eltrombopag) and overall for all enrolled subjects.

6.1 Demographics and Baseline Characteristics

Descriptive statistics with respect to subject characteristics at baseline will be displayed by prior TPO-RA (romiplostim and eltrombopag) and overall for all enrolled subjects. The variables to be summarized are:

Demographics

- Age at enrollment (years)
- Sex
- Race
- Ethnicity

Baseline subject characteristics

- TSQM domain scores of effectiveness, side effects, convenience, and global satisfaction
- Summary of WHO Bleeding Scale assessment (within the previous 7 days)
- Platelet count as assessed by local lab ($10^9/L$)

A listing of demographic and baseline characteristics will also be provided.

6.2 Medical History

Medical history will be coded using the Medical Dictionary for Regulatory Authorities (MedDRA) version 26.1 or later. The coding version may be updated prior to database lock if a newer version is available.

Medical history will be tabulated by Preferred Term (PT) by prior TPO-RA (romiplostim and eltrombopag) and overall for all enrolled subjects. Subjects with more than one medical history event in a PT will only be counted once per PT. Only those PTs with $>5\%$ of enrolled subjects will be displayed in the summary table. However, all medical history details will be provided in a data listing.

6.3 Immune Thrombocytopenia (ITP) History

Descriptive statistics with respect to ITP history will be displayed by prior TPO-RA (romiplostim and eltrombopag) and overall for all enrolled subjects. The variables to be summarized are:

- Time since ITP diagnosis (years), defined as (Date of enrollment – Date of Diagnosis+1)/365.25
- Number of platelet transfusions in the previous 1 year
- Number of previous hospitalizations for ITP
- Number of previous significant bleeding events
- History of splenectomy (yes/no)
- History of thromboembolic events (yes/no)

A listing of ITP history will also be provided. It will include the variables above along with the date of last platelet transfusion and the reason for switching to avatrombopag from eltrombopag or romiplostim.

